5.6.2 Anticipated Reactions

As this is a behavioral study, there are no ingested medications, and no biomedical procedures. It is unlikely that participants will be at any risk for physical harm as a result of study participation.

Participants may find some of the questions asked in the questionnaire to be emotionally upsetting, and may experience some fatigue from the length of the assessment battery. As this is a study targeting symptoms that are debilitating and interfere with quality of life, it is possible that some participants will experience depression and one of the major symptoms of depression, suicidality.

Participants may also find some of the breathing exercises from the dyspnea intervention uncomfortable during sessions and during home practice.

5.6.3 Reaction Management

Following the explanations by the study staff, participants will either sign a detailed consent form or provide verbal consent. The consent process will include all of the study procedures, information about potential risks and benefits of participation, and information regarding whom the participant can contact for further questions. It also will state that participation is voluntary, that participants can refuse to answer any question, that they can withdraw from the study at any time, and that study participation is in no way related to their medical care. The PI will review all informed consents within one week of their completion. All study staff will complete the required human subjects training before they are allowed to work on any human subject aspects of the study.

The need for further intervention and referral regarding anxiety and depression symptoms will be determined by clinical cutoffs on the subscales of the Hospital Anxiety & Depression Scale (HADS) and by clinical assessment of the trained study nurse should any participant note heightened emotional distress and/or suicidality. Both the anxiety and depression subscales scores of the HADS range from 0 to 21, with a score of 11 or greater indicating definitive anxiety or depression. A score of less than 7 is considered normal, and a score of 8-10 on each subscale suggests probable anxiety and depression. Study patients whose scores increase from the normal or probably range to the more severe range for depression (i.e., ≥ 11) will be called by qualified study staff (e.g., [name], a licensed clinical psychologist, or similarly trained designee) to determine if the patient requires further intervention for his or her mood symptoms. Study staff will also assess for any suicidal ideation and ensure that the patient is not at any risk for self-harm. If the patient needs further outpatient services for depression, including pharmacotherapy, or is at risk for self-harm requiring hospitalization, study staff will make the necessary referrals for treatment. For example, for patients who are distressed but in no danger to self or others, study staff will refer either to the MGH Oncology Social Work Service or to the MGH Ambulatory Psychiatric Services [contact]), including the Cognitive-Behavioral Therapy Program. If suicidality or risk of harm to others is otherwise discovered at any study visit, the participant will be referred to appropriate services. Specifically, in the case that hospitalization is required, study staff will contact and escort the patient to the MGH Acute Psychiatry Service [contact]), with the aid of the MGH Police & Security if necessary [contact]). Study staff assessments of patient distress and/or risk will be documented in the electronic medical record so that the clinical team is notified of any potential need for increased support.

If participants find the dyspnea intervention uncomfortable and/or upsetting during intervention sessions or during home practice, the participants or the study interventionists delivering the intervention may page the PI ([name]) at any time. [name] is a licensed clinical psychologist with extensive experience delivering cognitive behavioral treatments for individuals with advanced lung cancer (see previous clinical studies).

The PI, co-investigator team, and the nurse study interventionists will meet at least monthly to review study progress, ensure proper implementation of the intervention, and review any adverse reactions that occur. The PI and the study staff for this study will also meet weekly to review consents and collected data to ensure proper adherence to study protocol.

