6.0 STATISTICAL ANALYSIS

6.1 Study Endpoints

6.1.1 Primary and Secondary Endpoints

The primary outcome is comparison of the MMRCDS and CDS severity scores at 8-week post-assessment between study arms, controlling for baseline values.

The secondary outcomes will be comparison of quality of life, anxiety, depression, and activity level between study groups. To assess quality of life, we will compare the post-assessment (8-week) FACT-L scores between study arms, controlling for baseline values. To evaluate anxiety and depression symptoms, we will similarly compare the continuous scores as well as rates of depression and anxiety symptoms reported per HADS score at 8 weeks between study arms, controlling for baseline values. To assess activity level, we will compare the percentage of time spent immobile but awake on actigraphy and self-report weekly leisure-time physical activity score at 8 weeks between study groups, controlling for baseline values.

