Aim 2: To demonstrate the efficacy of the brief behavioral intervention for improving quality of life, anxiety, depression, and activity level (secondary outcomes) in patients with advanced lung cancer.

Hypothesis 2: Participants with advanced lung cancer who are randomly assigned to receive the brief behavioral intervention will experience statistically and clinically significant improvements in quality of life (FACT-L), anxiety and depression (HADS), as well as activity level (per self-report Godin-Shephard Leisure-Time Physical Activity Questionnaire and the percentage of time spent immobile but awake on actigraphy) compared to those assigned to usual care.

Analyses: The statistical significance of between-group differences for the continuous secondary outcomes will be assessed with general linear models (GLM) and linear mixed models, with appropriate covariates and an alpha level of .05. We will examine the between-group differences (i.e., intervention versus control) at 8-week post-assessment for each specific secondary outcome (all are continuous variables), controlling for baseline values. In the event that the effect of the intervention differs by cancer type, use of opiate medication or other patient characteristic, we will examine these variables as interaction terms in the GLM analysis. We will explore independent improvements in these secondary outcomes by adding changes in MMRCDS or CDS severity scores as a covariate. Finally, we will also again estimate practical and clinical significance of these outcomes (using Cohen's d and Reliability Change Index) and conduct linear mixed models to examine the trajectory of between-group differences in these variables across all study time points.

6.3.3 Aim 3

Aim 3: To explore mediators and moderators of the effect of the brief behavioral intervention on patient-reported outcomes.

Hypothesis 3: Intervention effects on patient-reported dyspnea will be mediated by improved mastery in managing breathlessness and potentially moderated by patient demographic and clinical factors (e.g., gender, age, opioid use, performance status, and disease comorbidity).

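### The HADS bands in section 5.6.3 leave a score of exactly 7 in no band, so the depression call rule, read literally, omits a patient who moves from 7 to 11 or more

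*Combined protocol and SAP*

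**What the plan says.** Section 5.6.3 (Reaction Management) states the scale and the top band together: "Both the anxiety and depression subscales scores of the HADS range from 0 to 21, with a score of 11 or greater indicating definitive anxiety" (the sentence goes on to include depression). The two lower bands follow: "A score of less than 7 is considered normal, and a score of 8-10 on each subscale suggests probable anxiety and depression".

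The call rule comes next and is defined by the band in which the patient starts: "Study patients whose scores increase from the normal or probably range to the more severe range for depression", with that severe range given as 11 and above. These patients are telephoned by qualified staff, who judge whether more help is needed for mood and ask about suicidal thoughts. The rule names depression only.

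The section also allows for assessment that does not depend on the bands, namely "by clinical assessment of the trained study nurse should any participant note heightened emotional distress and/or suicidality". It provides for referral if suicidality comes to light at a study visit, and it describes a weekly meeting of the principal investigator and staff that goes over collected data.

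**The concern.** A rule that starts from bands works only if the bands cover the scale. Here the normal band stops below 7 and the next begins at 8. A depression score of 7 is therefore neither normal nor probable as written, and a later rise to 11 or more does not start from a range that the rule recognises.

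What is at stake is the call itself, which is where mood and suicidal ideation are assessed. Section 5.6.2 accepts that some participants may become depressed or suicidal, so this is an operating safety rule and not background text. Someone who applies it mechanically would call a patient who rose from 6 and one who rose from 8, but not one who rose from 7.

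**Working it through.** No formula or power figure is involved. The check lists every possible score against the written bands and then against the call rule.

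**Inputs, all from section 5.6.3**
- Scale: 0 to 21. I take scores as whole numbers, as the bands themselves do (8-10 is followed directly by 11). That gives 21 - 0 + 1 = 22 possible scores.
- Normal: below 7.
- Probable: 8 to 10.
- Definitive: 11 and above.
- Call rule: a move from normal or probable to 11 or more, on depression.

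**Step 1: coverage of the scale**

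| Band | Scores | Count |
|---|---|---|
| Normal | 0-6 | 7 |
| Probable | 8-10 | 3 |
| Definitive | 11-21 | 11 |
| Total placed | | 7 + 3 + 11 = 21 |

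That leaves 22 - 21 = 1 score unplaced, and it is 7. No score falls in two bands.

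**Step 2: the call rule**

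There are 11 starting scores below the trigger range, 0 to 10. On a move to 11 or more:
- starts of 0-6 are in the normal band, so the rule is met (7 scores);
- starts of 8-10 are in the probable band, so the rule is met (3 scores);
- a start of 7 is in no band, so the rule is not met (1 score).

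The rule is met for 7 + 3 = 10 of 11 starting scores.

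**Step 3: effect of reconciling the text**

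Placing 7 in either neighbouring band gives 22 of 22 scores in exactly one band and 11 of 11 starting scores covered. The check does not favour one placement over the other.

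**Step 4: size**

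The patients affected are those with a depression score of 7 at one assessment and 11 or more at a later one. A count would need the distribution of depression scores in this population and the correlation between assessments. The documents give neither. The share of patients who score 7 at a single assessment would not answer the question, because most of them need never reach 11.

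**The case against.** The strongest reply is that this is a slip that nobody would act on. The trigger range is stated as 11 and above, the plain sense is any rise from below 11 into it, and no sensible member of staff would call for 6 and 8 but pass over 7. There is also nurse assessment when a participant reports distress, referral if suicidality is found at a visit, and the weekly review of data.

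Much of this stands, and it keeps the practical effect small. It does not correct the rule. The nurse route depends on the participant speaking up. Nurse sessions are scheduled only in the intervention arm and within eight weeks of enrollment (sections 5.3.2 and 5.5), so none is scheduled around the week 16 and 24 assessments. Follow-up questionnaires may come back by mail or through REDCap (sections 5.5 and 5.5.1). For a usual-care patient who posts the form, the score may be the only written trigger. The weekly meeting checks adherence to the protocol, and the protocol is where the gap lies.

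A reader might also infer more than the documents support:
- **That a 7 cannot be classed for the HADS rate endpoint.** Section 6.1.1 lists "rates of depression and anxiety symptoms reported per HADS score at 8 weeks" without a cutoff and without reference to section 5.6.3. If a rate were cut at either case boundary in that section, 8 or 11, a 7 would be a non-case and all 22 scores would be classed. It would be unclassed only if the rate used the three bands, or normal as its own category, and neither is stated. The missing case definition is a separate matter, as is the description of the secondary outcomes in section 6.3.2: "for each specific secondary outcome (all are continuous variables), controlling for baseline values". Placing the 7 would cure neither.
- **That anxiety scores are affected in the same way.** The band gap applies to both subscales, but the call rule is written for depression only.
- **That an automated alert is wrongly programmed.** Section 5.4.3 describes REDCap as data capture with type and range checks. No HADS alert is described.

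**Conclusion.** The gap is established from the text alone: 21 of 22 scores are placed, and 10 of 11 starting scores meet the depression call rule on reaching 11 or more. The exception in both cases is 7. The only assumption is that scores are whole numbers.

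The consequence is limited. It arises only for a patient who scores 7 on depression, later reaches 11 or more, and is handled by someone who follows the wording exactly. That number is small and cannot be derived from the documents. Nothing in them shows that a call has been missed, and no estimate, test or power figure depends on the point. It should still be corrected, because the error is in a rule that staff are meant to follow.

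**What to change.** Reconcile the bands and the call rule in section 5.6.3 so that every score from 0 to 21 falls in exactly one band and every starting score below the trigger range is covered. Where 7 belongs is for the clinical team to decide.

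Then do two checks. Confirm that whatever process applies the rule, manual or otherwise, follows the reconciled text. Review the depression scores already collected for any participant who moved from 7 to 11 or more without a call.

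The cost is about one line of protocol text and a short look through existing scores. Sample size, data collection and the primary analysis are unaffected.

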In addition to poor quality of life, dyspnea is linked to increased pain, anxiety, and mood disturbance among patients with cancer. In a cohort of 120 patients with early and late-stage lung cancers, approximately 87% reported experiencing dyspnea, and those with more severe symptoms also had worse pain and anxiety.²⁷ For some individuals, dyspnea is associated with feelings of panic and impending death.⁸ We found in our own investigation of patients with lung cancer that those with dyspnea were twice as likely to have panic attacks compared to those without respiratory symptoms.²⁸ Furthermore, investigators have observed that dyspnea is related to depression, anxiety, fatigue, cough, and decreased coping capacity in patients with cancer receiving palliative care services.²⁹ These studies underscore that the experience of dyspnea is multifaceted, involving physical and psychological factors, and requires comprehensive symptom assessment and management.

Dyspnea is Associated with Increased Service Utilization

Compounding the suffering experienced by patients and families, dyspnea is a major cause of healthcare utilization among individuals with cancer. Specifically, respiratory distress accounted for the greatest number of emergency department (ED) visits in patients with lung cancer (32% of visits) in one study of cancer-related ED utilization. Many of these patients were subsequently admitted to the hospital after ED evaluation.¹³ This trend persists throughout the course of disease, as dyspnea is the second most common reason for visits to the ED in the final two weeks of life for patients with cancer.¹² Data suggest that the median survival for patients with lung cancer who present to the ED with dyspnea is only four weeks.³⁰ In the ambulatory care setting, one study showed that over half of patients with lung cancer (57%) utilized many services across disciplines, such as pulmonary rehabilitation and physical therapy, given their high symptom burden.³¹ Thus, the Quality Oncology Practice Initiative of

the American Society of Clinical Oncology has identified the assessment and management of dyspnea as a key measure of quality cancer care.¹⁴

Novel Treatment Approaches for Dyspnea Are Greatly Needed

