5.5.2 Intervention Administration

Patients assigned to the brief behavioral intervention for dyspnea will participate in two sessions. The first session will occur at the patients' next scheduled clinic visit (either in the infusion suite or the outpatient clinic) via telephone, or via secure video following baseline data collection. The first session must occur within six weeks of the baseline data collection. Chemotherapy regimens for patients with advanced lung cancer are typically administered every two to three weeks. Thus, the six-week window will allow all enrolled patients to have a scheduled appointment, with additional time should their treatment be delayed for any reason (e.g., holidays or low blood counts). In the unlikely event that the patient is unable to come to the hospital for the first intervention session before the six-week window closes, the patient will be mailed the necessary study materials and receive the first session over the telephone or via secure video to remain in window. In the rare cases that the patient is still unable to complete the first session before the six-week window closes, the patient will be re-administered their baseline assessments either at their next appointment or by mail, telephone, or online via REDCap. Study procedures will reset from the new baseline assessment.

The second session will occur at the patient's subsequent clinic visit, over the telephone, or via secure video, within eight weeks of the baseline data collection.

Participants in both arms of the study will receive usual care for their dyspnea under the care of their clinicians.

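### HADS depression call rule (section 5.6.3) fires only on a rise to 11 or more, so a patient already at 11 or more at baseline who stays there never gets the call or its suicidal-ideation check

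*Combined protocol and SAP*

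**What the plan says.** Section 5.6.3 opens with a principle based on score level and covering both subscales: "The need for further intervention and referral regarding anxiety and depression symptoms will be determined by clinical cutoffs on the subscales" of the HADS. A second route is the study nurse's clinical assessment when a participant reports distress or suicidality. The section gives each subscale a range of 0 to 21, "with a score of 11 or greater indicating definitive anxiety or depression".

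One concrete action is then attached to a score: "Study patients whose scores increase from the normal or probably range to the more severe range for depression", glossed as 11 or more, are telephoned by a qualified person to judge whether they need further help. The next sentence adds the safety check: "Study staff will also assess for any suicidal ideation and ensure that the patient is not at any risk for self-harm". It has no trigger of its own. A further route does not depend on a score: "If suicidality or risk of harm to others is otherwise discovered at any study visit, the participant will be referred to appropriate services".

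The HADS is collected at baseline and at weeks 8, 16 and 24 (table in section 5.4.1). It is in both the full and the abbreviated questionnaire packets (section 5.5.1).

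**The concern.** The principle concerns where a score stands, but the working rule concerns how it has moved. A patient who enters at 11 or more and remains there has the score that the protocol calls definitive, yet has made no upward move, so staff who follow the rule exactly do not call.

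Such patients are foreseeable. Entry requires dyspnea, and section 1.2 says that "dyspnea is linked to increased pain, anxiety, and mood disturbance among patients with cancer". Section 5.6.2 accepts that "it is possible that some participants will experience depression and one of the major symptoms of depression, suicidality". The exclusions in section 3.1.2 contain no HADS limit. They remove only patients whose psychiatric or cognitive condition prevents consent or participation, and those whom a treating clinician considers unsuitable.

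The stake is patient safety. The study could record definitive depression at every assessment without the score ever prompting the suicidal-ideation check.

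**Working it through.** The plan gives no figure to reproduce. This is a logic check of the trigger and carries no probabilities.

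**Inputs.** Four scheduled HADS depression scores: baseline and weeks 8, 16 and 24 (section 5.4.1). Threshold 11 and the rise trigger: section 5.6.3. Code each score L (below 11) or H (11 or more). A call occurs when an L is followed directly by an H.

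**Step 1: all patterns.**
- Possible patterns: 2^4 = 16.
- With at least one H: 16 − 1 = 15.
- With at least one H but no L-to-H step: HHHH, HHHL, HHLL, HLLL, which is 4.
- With a call: 15 − 4 = 11.

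**Step 2: split by baseline.**
- Baseline L, later H: 7 patterns, all called.
- Baseline H: 8 patterns. Four are called (HHLH, HLHH, HLHL, HLLH) and four are not (those in step 1).
- Check: 7 + 4 = 11.

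The gap is therefore confined to patients at 11 or more at baseline. Those who are called must first fall below 11 and then rise again, so on the scheduled assessments their first call comes at week 16 (HLHH, HLHL) or week 24 (HHLH, HLLH). The case of most concern is HHHH. HLLL is milder, since that patient is below 11 by week 8.

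**Step 3: one exception.** If the first session misses its six-week window, "the patient will be re-administered their baseline assessments" (section 5.5.2). That could add a score and might happen to show a rise. The protocol describes it as rare.

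**Step 4: worked case.** Depression 10 then 11: one call. Depression 21 at all four assessments: 4 definitive scores, 0 score-triggered calls.

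**Step 5: other cover, set beside the gap.**

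| Route | Section | What sets it off |
|---|---|---|
| Nurse assessment | 5.6.3 | The participant reports distress or suicidality |
| Referral | 5.6.3 | Suicidality found in some other way at a visit |
| Paging the PI | 5.6.3 | The intervention is uncomfortable or upsetting |
| Weekly data review | 5.6.3 | Its stated purpose is protocol adherence; not calling this patient is adherent |
| Note in the medical record | 5.6.3 | A staff assessment has taken place |
| Email to the oncology clinician | 5.5 | A positive dyspnea screen, not a HADS score |

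None is set off by a stable high score. Scheduled nurse sessions exist only in the intervention arm (section 5.5). Usual-care patients are offered a clinician meeting only after the final follow-up (section 5.3.3). Follow-up questionnaires may come back by mail or online (section 5.5.1), which leaves less chance of discovery at a visit.

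**Step 6: effect of a level trigger.** With a call on any H, all 15 patterns in step 1 receive at least one call.

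**Step 7: scale of the extra work.** The share of patients at 11 or more at baseline is not in the documents. Assuming 5% to 20% of the planned 220: 220 × 0.05 = 11 and 220 × 0.20 = 44 first baseline calls.

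**The case against.** The strongest reply is that the opening cutoff sentence is itself the rule, and the call is one worked-out pathway under it. On that reading a persistent depression score of 11 or more remains grounds for referral, and only the procedure is missing. Part of this stands: the sentence does show an intent to cover high scores on both subscales. But it names no person, step or time for a stable high score, whereas the trigger that is spelled out passes that patient over. Staff who follow the explicit rule get the less safe result.

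A second reply is that section 5.6 concerns adverse reactions, so detecting deterioration is a reasonable aim, and both arms remain under usual clinical care. A rise trigger does fit that heading. It does not fit the section's own cutoff principle, and the study itself collects the baseline score.

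A third reply is that the patient at 21 throughout is an extreme and the pattern count says nothing about frequency. That is correct. Both show what the rule does, not how often.

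A reader might infer two stronger claims that the documents do not support:

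- **That severely depressed patients have no cover.** They have several routes (working, step 5), as well as the entry exclusions and the investigators' meetings, held at least monthly, to review adverse reactions. What is missing is a route prompted by the score.
- **That anxiety of 11 or more is an equal gap and needs the same call.** The anxiety score has no stated action, but the concern in section 5.6.2 is depression and suicidality. A suicidal-ideation call for anxiety alone would go beyond it.

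**Conclusion.** The point holds for depression. Followed as written, section 5.6.3 never gives the score-triggered call, or its suicidal-ideation check, to a patient who is at 11 or more at baseline and stays there. Of the 15 score patterns containing a definitive score, 4 bring no call, and all 4 begin at 11 or more. How many patients this means cannot be derived, because the documents give no distribution of baseline HADS scores.

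The conclusion assumes that the call sentence is read literally, as a rise into the range, and that the suicidal-ideation sentence belongs to that call. No other section contains a score-based rule that closes the gap.

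This is a safety weakness worth correcting. It does not affect sample size or the validity of the primary comparison. The missing action for anxiety is a secondary matter of clarification.

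**What to change.** Replace the trigger in section 5.6.3 with wording such as: *Any participant who scores 11 or more on the HADS depression subscale at any assessment, baseline included, will be telephoned by a qualified member of the study team, who will ask about suicidal thoughts; a repeat call may be omitted if the same elevation has already been assessed.* The condition for omitting a repeat is assessment, not referral, so that a patient judged not to need referral is not called again each time. Apply the rule identically in both arms, record calls and referrals by arm, and keep the existing nurse and visit routes.

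For anxiety of 11 or more, state the action that the opening cutoff sentence implies, for example notifying the care team.

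**Cost.** A short wording change and some additional calls. No new data are needed, and the callers and referral routes already exist. The 11 to 44 calls in the working cover first baseline calls for depression only; notifications for anxiety would be extra.

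**Trade-off.** Extra referrals in both arms could slightly narrow the group differences on HADS anxiety and depression, which are secondary outcomes at week 8 (section 6.1.1). Dyspnea might also be touched: section 5.6.3 names a cognitive-behavioral therapy program as a referral destination, and the study intervention draws on the same model (section 5.3.2). The documents do not allow either effect to be sized.
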